6.4.3.1 Spontaneously report of symptoms of paraesthesia

If the patient spontaneously reports cutaneous sensations such as tingling, pins and needles, prickling, skin crawling, formication, burning sensation and numbness, a more thorough questioning will be done, asking for frequency, start of symptoms in relation to drug intake, duration of symptoms and level of discomfort. The responses should be recorded in the paraesthesia module in the eCRF. Furthermore, a complete physical examination including neurological examination with evaluation of cranial nerve functions must be completed and documented in the eCRF by the investigator.

If the patient reports episodes of symptoms of paraesthesia for 7 consecutive days the patient will permanently stop intake of IP (see Section 5.8.1), and be referred to a board certified neurologist for evaluation. A copy of the report from the neurologist must be provided to the AstraZeneca representative (ICON).

6.4.3.2 Active questioning of specific symptoms

Following the spontaneous AE collection, there will be active questioning to determine whether patients experienced any episode of the following: syncope, felt faint, lightheadedness or dizziness. In order to get baseline information before study treatment has started, the question will also be asked prior to first intake of IP at visit 2. All reported

episodes will be recorded in a specific module in the eCRF. Reported episodes that fulfil any of the SAE criteria (see Section 6.4.2) or are the reason for discontinuation from the study will be recorded in the AE module in the eCRF.

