Appendix I	Overall Treatment Evaluation (OTE) ePRO wording – US English

LIST OF ABBREVIATIONS AND DEFINITION OF TERMS

The following abbreviations and special terms are used in this study Clinical Study Protocol

Abbreviation or special term	Explanation
AE	Adverse event (see definition in Section 6.4.1)
ALP	Alkaline phosphatase
ALT	Alanine aminotransferase
AMA	Anti-Mitochondrial antibodies
ANA	Anti-nuclear antibodies
anti-EBV-IgM	Epstein-Barr Virus antibodies immunoglobulin M
anti-CMV-IgM	Cytomegalo Virus antibodies immunoglobulin M
anti-HAV-IgM	Hepatitis A Virus antibodies immunoglobulin M
anti-HBc-IgM	Hepatitis B Virus core antigen immunoglobulin M
anti-HCV	Hepatitis C Virus antibodies
ASA	Acetylsalicylic acid
AST	Aspartate aminotransferase
AUC	Total area under the plasma concentration vs. time curve
BIL	Bilirubin
BMI	Body Mass Index
BP	Blood pressure
BUN	Blood urea nitrogen
C _{max}	Observed maximum plasma concentration
CDT	Carbohydrate deficient transferrin
CK	Creatine kinase
CMV	Cytomegalo Virus
CNS	Central nervous system
COC	Combined oral contraceptive
COX-2	Cyclo-oxygenase-2
CRF	Case Report Form (electronic/paper)
CRP	C-reactive protein
CSA	Clinical Study Agreement
CSP	Clinical Study Protocol

Abbreviation or special term	Explanation
CSR	Clinical Study Report
CT	Computer tomography
DAE	Discontinuation of Investigational Product due to Adverse Event
dECG	Digital electrocardiogram
DBP	Diastolic blood pressure
DNA	Deoxyribonucleic acid
DSMB	Data safety monitoring board
DUS	Disease under study
EBV VCA IgM	Epstein-Barr Virus Viral Capsid Antigen immunoglobulin M
EBNA IgG	Epstein-Barr Nuclear Antigen immunoglobulin G
EC	Ethics Committee, synonymous to Institutional Review Board (IRB) and Independent Ethics Committee (IEC)
ECG	Electrocardiogram
eCRF	Electronic case report form
e-diary	Electronic diary
ePRO	Electronic patient-reported outcome(s)
ES	Effect size
FAS	Full analysis set
FDA	Food and Drug Administration
GABA _B	Gamma-Amino-Butyric-Acid B receptor
GCP	Good Clinical Practice
GERD	Gastroesophageal Reflux Disease
GI	Gastrointestinal
GMP	Good Manufacturing Practice
Hb	Haemoglobin
HBsAg	Hepatitis B Virus surface antigen
H.pylori	Helicobacter pylori
HR	Heart rate
HRT	Hormone replacement therapy
IATA	International air transport association
IB	Investigator's Brochure
IBS	Irritable Bowel Syndrome

Abbreviation or special term	Explanation
ICC	Intraclass correlation coefficients
ICH	International Conference on Harmonisation

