5.8 Discontinuation of investigational product

Patients may be discontinued from IP in the following situations:

- Patient decision. The patient is at any time free to discontinue treatment, without prejudice to further treatment
- AE
- Severe non-compliance to study protocol
- Incorrectly randomized patient, see Section 5.3
- Development of any of the following study specific criteria for individual patients, which **must** lead to discontinuation of IP:
 - Patient experiencing symptoms of paraesthesia daily for at least 7 consecutive days, see Section 6.4.3.1
 - Patient experiencing a syncopal episode (loss of consciousness) from any cause
 - Patient describing an AE of pre-syncope or dizziness as severe. Orthostatic dizziness provoked during testing would not automatically discontinue a patient unless this continued without provocation from orthostatic testing (eg at home when getting up)
 - Patient with a corrected QT interval (QTcF) ≥ 500 ms
 - Patient with ALT or AST $> 5 \times$ ULN, see Section 6.4.5.2

- Patient with ALT or AST >3 x ULN in combination with BIL >2 x ULN, see Section 6.4.5.2
- Patient with ALT or AST >3 x ULN and clinical signs or symptoms indicating liver dysfunction, see Section 6.4.5.2
- AstraZeneca may decide to stop a dose group in the study based on a recommendation from the DSMB. The following criteria, included in the DSMB charter, serve as a guide for the DSMB to stop a dose group. However, a more restrictive approach may be applied based on the DSMB's and AstraZeneca's evaluation during the study:
 - two or more unique events of syncope in different patients in the same dose group that cannot definitively be attributed to another cause (eg, syncope while having blood drawn would be attributable to the blood draw, not the investigational product)
 - corrected QT interval (QTcF) \geq 500 ms in 20% of the planned total number of patients to be enrolled in the same dose group.
 - dizziness causing discontinuation from the IP in 10% of the planned total number of patients to be enrolled in the same dose group.

If a dose group is stopped, any treatment group(s) on a higher dose will also be stopped.

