If a decision has been taken to stop a dose group the investigator will receive information about which patients (randomization codes) should be discontinued from treatment. The investigator at each site must immediately inform the patient to stop intake of the IP and to schedule an end of treatment visit within 1 week and a subsequent end of study visit. The investigator must also ensure that no new patients will be randomized to the stopped dose group. Patients on lower doses of IP and placebo will continue in the study unless the site is informed otherwise.

In all patients discontinued from the IP, data collection and procedures should continue as described in Section 5.8.1. If the patient does not agree to attend an end of treatment visit, a modified follow up should be arranged (eg, telephone contact to follow-up with respect to any ongoing AEs or a reminder to return the e-diary device and unused IP), if agreed to by the patient and in compliance with local data privacy laws/practices. Relevant information should be recorded in the unscheduled visit section in the eCRF.

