6.4.3 Recording of adverse events

Time period for collection of adverse events

Non serious AEs will be collected from the first time of administration of IP throughout the treatment period and including the follow-up period. SAEs will be recorded from the time of signed informed consent throughout the treatment period and including the follow-up period.

Follow-up of unresolved adverse events

Any AEs that are unresolved at patient's last AE assessment in the study are followed up by the investigator for as long as medically indicated, but without further recording in the eCRF. AstraZeneca retains the right to request additional information for any patient with ongoing AE(s)/SAE(s) at the end of the study, if judged necessary.

Variables

The following variables will be recorded in the eCRF for each AE:

- AE (verbatim)
- the date when the AE started and stopped
- maximum intensity
- whether the AE is serious or not
- investigator causality rating against the IP (yes or no)
- action taken with regard to IP
- AE caused patient's withdrawal from study (yes or no)
- outcome.

In addition, the following variables will be collected for SAEs:

- date AE met criteria for serious AE
- date investigator became aware of serious AE
- AE is serious due to

- date of hospitalization (as applicable)
- date of discharge (as applicable)
- probable cause of death (as applicable)
- date of death (as applicable)
- autopsy performed (as applicable)
- causality assessment in relation to study procedure(s)
- causality assessment in relation to other medication
- description of AE.

Intensity rating is defined as:

- mild (awareness of sign or symptom, but easily tolerated)
- moderate (discomfort sufficient to cause interference with normal activities)
- severe (incapacitating, with inability to perform normal activities).

It is important to distinguish between serious and severe AEs. Severity is a measure of intensity whereas seriousness is defined by the criteria in Section 6.4.2. An AE of severe intensity need not necessarily be considered serious. For example, nausea that persists for several hours may be considered severe nausea, but not a SAE. On the other hand, a stroke that results in only a limited degree of disability may be considered a mild stroke but would be a SAE.

Causality collection

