The investigator will assess causal relationship between investigational product and each AE, and answer “yes” or “no” to the question “Do you consider that there is a reasonable possibility that the event may have been caused by the investigational product?”

For SAEs causal relationship will also be assessed for other medication and study procedures. Note that for SAEs that could be associated with any study procedure the causal relationship is implied as “yes”.

A guide to the interpretation of the causality question is found in [Appendix B](#) to the CSP.

Adverse Events based on signs and symptoms

All AEs spontaneously reported by the patient or reported in response to the open question from the study personnel: “Have you had any health problems since the previous visit/you were last asked?”, or revealed by observation will be collected and recorded in the eCRF.

When collecting AEs, the recording of diagnoses is preferred (when possible) to recording a list of signs and symptoms. However, if a diagnosis is known and there are other signs or symptoms that are not generally part of the diagnosis, the diagnosis and each sign or symptom will be recorded separately.

See Section 5.8 regarding discontinuation criteria.

Adverse Events based on examinations and tests

The results from protocol mandated laboratory tests and vital signs will be summarised in the clinical study report (CSR). Deterioration as compared to baseline in protocol-mandated laboratory values, vital signs, ECGs should therefore only be reported as AEs if they fulfil any of the SAE criteria or are the reason for discontinuation of treatment with the IP.

If deterioration in a laboratory value/vital sign is associated with clinical signs and symptoms, the sign or symptom will be reported as an AE and the associated laboratory result/vital sign will be considered as additional information. Wherever possible the reporting investigator uses the clinical, rather than the laboratory term (eg, anaemia versus low haemoglobin value). In the absence of clinical signs or symptoms, clinically relevant deteriorations in non-mandated parameters should be reported as AE(s).

Deterioration of a laboratory value, which is unequivocally due to disease progression, should not be reported as an AE/SAE.

Any new or aggravated clinically relevant abnormal medical finding at a physical examination as compared with the baseline assessment will be reported as an AE.

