6.4.3.3 Disease under study

The following symptoms of disease under study are not to be reported as AEs during treatment with IP unless they fulfil the criteria for SAEs or lead to early discontinuation of the IP. These are considered as symptoms of disease under study and are measured outcome variables of interest in the study:

- a burning feeling behind the breastbone
- pain behind the breastbone
- a burning feeling in the centre of the upper stomach
- a pain in the centre of the upper stomach
- an acid taste in the mouth
- unpleasant movement of material upwards from the stomach
- burping (gas coming from the stomach through the mouth)
- hoarseness
- cough
- difficulty swallowing
- a bitter taste in the mouth
- stomach contents (liquid or food) moving upwards to the throat or mouth
- heartburn.

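### Section 6.4.3.2 ties AE-module entry of solicited syncope and dizziness episodes to leaving the study, where the protocol's related rules refer to stopping the IP

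*Protocol*

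**What the plan says.** Section 6.4.3.2 has patients asked directly about syncope, feeling faint, lightheadedness and dizziness once spontaneous AE collection is done. Every reported episode goes into a dedicated eCRF module. Those that fulfil an SAE criterion "or are the reason for discontinuation from the study will be recorded in the AE module in the eCRF".

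Two neighbouring rules do the same job for other findings. For protocol-mandated laboratory values, vital signs and ECGs, section 6.4.3 makes a deterioration an AE if it is serious or if such findings "are the reason for discontinuation of treatment with the IP". For symptoms of reflux disease, section 6.4.3.3 excludes them from AE reporting "unless they fulfil the criteria for SAEs or lead to early discontinuation of the IP". The abbreviation list expands DAE as "Discontinuation of Investigational Product due to Adverse Event".

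Section 5.8 lists findings that must lead to stopping the IP. One is "Patient experiencing a syncopal episode (loss of consciousness) from any cause". The same section adds: "In all patients discontinued from the IP, data collection and procedures should continue as described in Section 5.8.1". Section 5.9 treats withdrawal from the study as something else, namely the end of both IP and assessments.

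**The concern.** Of the three rules that decide when a finding becomes a reportable AE, only the one for solicited haemodynamic symptoms is tied to leaving the study. The protocol gives no reason for the difference. These are also the symptoms for which direct questioning was added, after the pulse increases, postural dizziness and shortened tilt-test endurance described in section 1.4.

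A patient who stops the IP is expected to stay in follow-up. That patient has discontinued the IP but has not left the study, so on the literal wording the second condition in 6.4.3.2 is not met. If the episode is not serious either, nothing in that section requires an AE entry, and without an AE there is no DAE. The ongoing surveillance in section 12.4 is described largely through AEs and DAEs. What is at stake is whether an IP stop for a solicited haemodynamic symptom is labelled correctly and reaches those reviews on time.

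**Working it through.** No sample size, power or error-rate figure is involved, so the check is a comparison of texts.

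**Step 1: which event does each rule use?**

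| Place in the protocol | Subject | Event other than seriousness |
|---|---|---|
| 6.4.3 | mandated laboratory values, vital signs, ECG | stopping the IP |
| 6.4.3.3 | symptoms of the disease under study | stopping the IP |
| Abbreviation list | definition of DAE | stopping the IP |
| 5.8, DSMB guide | dizziness | stopping the IP |
| 6.4.3.2 | solicited syncope, faintness, lightheadedness, dizziness | leaving the study |

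The dizziness guide in 5.8 is 10% of the patients planned for a dose group. With 130 planned per group (section 12.3), that is 0.10 × 130 = 13 patients who stop the IP for dizziness.

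**Step 2: are the two events the same in this protocol?** They are not. After an IP stop, 5.8 keeps data collection going, and 5.8.1 asks for an early end-of-treatment assessment and strongly encourages visit 7. Section 5.9 covers the patient who gives up both IP and assessments. The AE record in 6.4.3 holds them as two variables: "action taken with regard to IP", and whether the AE caused the patient's "withdrawal from study (yes or no").

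**Step 3: which episodes could fall through?** Other routes into the AE module have to be taken out first.

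- Anything reported spontaneously, in answer to the open health question, or seen by observation is an AE under 6.4.3. Active questioning comes after that step and is not among those routes.
- Symptoms that occur during the orthostatic test are AEs under 6.4.3.4.
- Severe pre-syncope or dizziness is a mandatory IP stop in 5.8, and that criterion is itself worded as an AE. Such a case is already classed as an AE when it triggers the stop.
- A serious episode meets the first condition of 6.4.3.2.

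What remains is an episode that is non-serious, raised only on direct questioning after the first dose, and the reason for stopping the IP in a patient who stays in the study. Syncope that does not meet an SAE criterion shows the mismatch best. Section 5.8 obliges the site to stop the IP, while 6.4.3.2 requires the AE entry only through a study exit that need not happen.

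**Step 4: what does such an episode miss, and what does it not miss?** Section 12.4 describes weekly updates on AEs and discontinuations due to AEs, a two-weekly joint review of blinded data that include AEs, SAEs and DAEs, and a continual DSMB survey of DAEs and SAEs. A non-serious episode with no AE entry can be absent from those AE and DAE counts. It is still in the specific module, the DSMB receives data regularly and reviews all safety data at least twice, and the dose-AE regression in 12.2.4 merges spontaneous and solicited reports.

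**The case against.** The strongest reply is that IP discontinuation was plainly meant. Section 6.4.7 also speaks loosely of discontinuing a patient from the study when it refers to the discontinuation criteria, and those criteria concern the IP. Section headings generally use discontinuation for the IP and withdrawal for the study. This argument stands as evidence of intent. It does not make the recording rule right, because sites and eCRF builders work from the written rule.

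A second reply is that other provisions nearly close the gap. Besides the routes listed above, AE collection is scheduled at every visit, and 5.8.1 has patients who decide to stop the IP asked for their reasons and any AEs. That also stands in large part, and it is why the residual case is narrow. The question in 5.8.1 is directed at patients who choose to stop, however, and a mandatory stop for syncope is not the patient's choice. Nor does 5.8.1 set a rule for the AE module.

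Three stronger readings are tempting, and the documents do not support them.

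- A reader might infer that 6.4.3.2 forbids AE entry for any other solicited episode. It does not. It is a positive instruction, without the restrictive wording of 6.4.3 and 6.4.3.3. The gap is a missing requirement.
- A reader might infer that safety data are lost or that patients are less protected. The episodes are kept in the specific module, and the mandatory stops in 5.8 apply whichever module is used.
- A reader might infer that the DSMB stopping guides fail. They count syncope events and IP stops for dizziness and are not tied to the AE module, so the DSMB can apply them from any source that holds the information.

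**Conclusion.** The trigger in 6.4.3.2 is wrong as written, with minor impact. It conflicts with both parallel recording rules, the DAE definition and the dizziness guide in 5.8, in a protocol that keeps IP discontinuation and study withdrawal apart.

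The consequence is limited to timely and correct DAE reporting to the surveillance in 12.4, for the narrow class of episodes identified above. It rests on two assumptions: that sites follow the wording literally, and that no other route brings the episode in as an AE. The protocol gives no frequency for such cases, so the number of patients affected cannot be estimated. Trial size and meeting frequency do not measure it either. No efficacy analysis is affected.

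**What to change.** In section 6.4.3.2, replace discontinuation from the study with discontinuation of the IP as the second condition for AE-module entry. That brings it into line with 6.4.3, 6.4.3.3 and the DAE definition. Any eCRF completion instruction that repeats the phrase should follow.

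The change is one phrase. Its only downside is at most a slight rise in AE and DAE counts for these terms.

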6.4.3.3 Disease under study

The following symptoms of disease under study are not to be reported as AEs during treatment with IP unless they fulfil the criteria for SAEs or lead to early discontinuation of the IP. These are considered as symptoms of disease under study and are measured outcome variables of interest in the study:

- a burning feeling behind the breastbone
- pain behind the breastbone
- a burning feeling in the centre of the upper stomach
- a pain in the centre of the upper stomach
- an acid taste in the mouth
- unpleasant movement of material upwards from the stomach
- burping (gas coming from the stomach through the mouth)
- hoarseness
- cough
- difficulty swallowing
- a bitter taste in the mouth
- stomach contents (liquid or food) moving upwards to the throat or mouth
- heartburn.

6.4.3.4 Recording of adverse events in connection with orthostatic test

A change in BP or pulse during an orthostatic test without accompanying symptoms should not be recorded as an AE. Other signs and symptoms occurring during the orthostatic test should be reported as AEs. Dizziness occurring in upright position during an orthostatic test should be reported as postural dizziness.

6.4.4 Reporting of serious adverse events

All SAEs have to be reported, whether or not considered causally related to the investigational product, or to the study procedure(s). All SAEs will be recorded in the eCRF.

If any SAE occurs in the course of the study, then investigators or other site personnel must inform appropriate AstraZeneca representative (ICON) within one day ie, immediately but **no later than the end of the next business day** of when he or she becomes aware of it.

The designated AstraZeneca representative (ICON) works with the investigator to ensure that all the necessary information is provided to the AstraZeneca Patient Safety data entry site **within one calendar day** of initial receipt for fatal and life threatening events **and within five calendar days** of initial receipt for all other SAEs.

For fatal or life-threatening adverse events where important or relevant information is missing, active follow-up is undertaken immediately. Investigators or other site personnel inform AstraZeneca representatives (ICON) of any follow-up information on a previously reported SAE within one calendar day ie, immediately but **no later than the end of the next business day** of when he or she becomes aware of it.

Once the investigators or other site personnel indicate an AE is serious in the WBDC system, an automated email alert is sent to the designated AstraZeneca representative (ICON).

If the WBDC system is not available, then the investigator or other study site personnel reports a SAE to the appropriate AstraZeneca representative (ICON) by telephone or fax. The AstraZeneca representative (ICON) will advise the investigator/study site personnel how to proceed.

The reference document for definition of expectedness/listedness is the IB for the AstraZeneca drug AZD3355.

